3.2 Exclusion Criteria

3.2.1 Both arms: Patients should not have received metformin within 6 months prior to registration.

Arm B: Patients who were on metformin while on PD-1/PD-L1 inhibitors are not eligible.

3.2.2 Patients should not have received prior immunotherapies (exception: prior PD-1/PD-L1 inhibitors are allowed for arm B only).

NOTE: Prior cancer vaccine treatments are permitted. For arm B, exposure to PD-1/PD-L1 inhibitors given as either a single agent or in combination with chemotherapy are allowed ≥ 14 days from registration.

NOTE: Immunotherapies include but are not limited to interleukin-2 and other immune checkpoint antagonist targeting CTLA-4, LAG-3, TIM-3, KIR etc. and/or agonists targeting OX40, ICOS, CD137, etc.

3.2.3 Patients who are intolerant to PD-1/PD-L1 inhibitors and/or metformin are excluded.

3.2.4 Patients with active autoimmune disease or history of autoimmune disease that might recur, which may affect vital organ function or require immune suppressive treatment including chronic prolonged systemic corticosteroids (defined as corticosteroid use of duration one month or greater), should be excluded. These include but are not limited to patients with a history of:

- immune related neurologic disease
- multiple sclerosis
- autoimmune (demyelinating) neuropathy
- Guillain-Barre syndrome
- myasthenia gravis
- systemic autoimmune disease such as SLE
- connective tissue diseases
- scleroderma
- inflammatory bowel disease (IBD)
- Crohn's
- ulcerative colitis
- patients with a history of toxic epidermal necrolysis (TEN)
- Stevens-Johnson syndrome
- anti-phospholipid syndrome

NOTE: Subjects with vitiligo, type I diabetes mellitus, residual hypothyroidism due to autoimmune condition only requiring hormone replacement, psoriasis not requiring systemic treatment, or conditions not expected to recur in the absence of an external trigger are permitted to enroll.

NU Study Number: NU 16L04
Other Study Number: CA 209-801

3.2.5 Patients are ineligible who have any condition requiring systemic treatment with corticosteroids (>10mg daily prednisone equivalents) or other immunosuppressive medications ≤14 days prior to registration.

NOTE: Inhaled steroids and adrenal replacement steroid doses >10mg daily prednisone equivalents are permitted in the absence of active autoimmune disease. A brief (less than 3 weeks) course of corticosteroids for prophylaxis (eg, contrast dye allergy) or for treatment of non-autoimmune conditions (eg, delayed-type hypersensitivity reaction caused by a contact allergen) is permitted.

3.2.6 Patients who have an uncontrolled intercurrent illness including, but not limited to any of the following, are not eligible:

- Uncontrolled hypertension – blood pressure ≥ 150/90 mmHg despite medical therapy
- Ongoing or active infection requiring systemic treatment
- Symptomatic congestive heart failure
- Unstable angina pectoris
- Cardiac arrhythmia
- Psychiatric illness/social situations that would limit compliance with study requirements
- Any other illness or condition that the treating investigator feels would interfere with study compliance or would compromise the patient's safety or study endpoints

3.2.7 Patients must not have had another primary malignancy within 2 years prior to starting study treatment with the exception of adequately treated basal cell carcinoma, squamous cell carcinoma or other non-melanomatous skin cancer, or in-situ carcinoma of the uterine cervix, or any local cancers that are deemed to be cured from investigator's point of view.

3.2.8 Patients may not be receiving any other investigational agents ≤ 14 days from registration.

3.2.9 Patients with known history of testing positive for human immunodeficiency virus (HIV) or known acquired immunodeficiency syndrome (AIDS) are excluded.

3.2.10 Patients who have any positive test for Hepatitis B or Hepatitis C virus indicating acute or chronic infection are excluded.

3.2.11 Patients with known diabetes whose glucose control or general health condition may be adversely affected by the use of metformin as per the study protocol as deemed by either the study investigator or endocrinologist are excluded.

3.2.12 Patients must not have any of the following contraindications to metformin:

- Hypersensitivity to metformin or any component of the formulation
- Kidney dysfunction or abnormal creatinine (Cr < 2ng/mL) from any cause
- Acute or metabolic acidosis

NU Study Number: NU 16L04
Other Study Number: CA 209-801

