1.5 Metformin

1.5.1 Clinical safety, Development and Efficacy

Metformin is a well-studied drug, utilized by a large number of adults with diabetes. The following are considered contraindications to the use of metformin: hypersensitivity to metformin or any component of the formulation; kidney dysfunction (serum creatinine ≥ 1.5 mg/dL in males or ≥ 1.4 mg/dL in females) or abnormal creatinine clearance from any cause (including shock, acute myocardial infarction, or septicemia); acute or chronic metabolic acidosis. In addition, it is generally recommended to temporarily discontinue metformin in patients undergoing radiologic studies in which intravascular iodinated contrast media are utilized. It is also recommended that metformin be used cautiously in patients with congestive heart failure requiring pharmacologic management, because the risk of lactic acidosis may be increased secondary to hypoperfusion.

Metformin was developed as an anti-diabetes drug. However, recent research have found interesting anti-tumor properites of metformin. Of note, the immune modulating properties leading to significant anti-tumor effect has not yet been explored in a clinical trial setting.

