3.0 PATIENT ELIGIBILITY

The target population for this study is all patients with advanced non-small cell lung cancer with and without prior exposure to PD-1 or PD-L1 inhibitors. This trial will be conducted at Northwestern University with the potential of opening the trial at other institutions.

A total of 51 subjects will be needed for this trial. Approximately 4 potentially eligible patients are seen per month, and it is anticipated that at least 2 per month will be accrued. Potential patients may be referred to the Principal Investigator (PI) at Northwestern University, [name], at [contact] or [contact].

Eligibility will be evaluated by the study team according to the following criteria. Eligibility waivers are not permitted. Subjects must meet all of the inclusion and none of the exclusion criteria to be registered to the study. Study treatment may not begin until a subject is registered. Please refer to Section 11.3 for complete instructions regarding registration procedures.

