3.1 Inclusion Criteria

- 3.1.1** Patients must have histologically confirmed, locally advanced or metastatic stage IV or non-resectable stage III non-small cell lung cancer (NSCLC).
- 3.1.2** Patients may have received any number and type of prior treatment regimens for their NSCLC (aside from patients in Arm A, who cannot have had PD-1/PD-L1 inhibitors).
- 3.1.3** Arm A: patients must be treatment naive to PD-1/PD-L1 inhibitors including but not limited to durvalumab, pembrolizumab, atezolizumab, nivolumab, and avelumab.

Arm B: patients' tumor must be either refractory to or progressed on one of the above agents.

NOTE: Prior treatment may include any number of PD-1/PD-L1 inhibitor therapies given as either a single-agent or in combination with chemotherapy..

NOTE: Patients must be eligible to receive the next line of therapy and not be suspected of having pseudoprogression. Both cases are defined by initial PD or PD after CR, PR, or SD using RECIST criteria, respectively.

NU Study Number: NU 16L04
Other Study Number: CA 209-801

3.1.4 Patients must have measurable disease according to the standard RECIST version 1.1.

NOTE: CT scans or MRIs used to assess the measurable disease must have been completed with 28 days prior to the study drug initiation.

3.1.5 Patients need to have adequate kidney, bone marrow, and liver functions ≤ 14 days of registration as specified below:

absolute neutrophil	$\geq 1,000/\text{mCL}^*$
platelets	$\geq 50,000/\text{mCL}^*$
hemoglobin	$\geq 8 \text{ g/dL}$
total bilirubin	≤ 1.5 times the institutional upper limit of normal (ULN) (or ≤ 3 times ULN in case of liver metastasis or Gilbert Syndrome)
AST(SGOT)/ALT(SPGT)	$\leq 2.5 \times$ institutional ULN (or ≤ 5 times ULN in case of liver metastasis)
creatinine	$\leq 1.4 \text{ ng/mL}$ for females; $\leq 1.5 \text{ ng/mL}$ for males** ng/ml

*Transfusion and/or growth factor are permitted within any timeframe.

**Patients with creatinine $\leq 2.0 \text{ ng/mL}$ may still be eligible if in the opinion of the investigator, the benefits of treatment outweigh the risks.

3.1.6 Patients must be age ≥ 18 years; both male and female are eligible.

3.1.7 Patients must exhibit an ECOG performance status of ≤ 2 .

3.1.8 Patients must have the ability to understand and the willingness to sign a written informed consent prior to registration on study.

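### The creatinine threshold in exclusion 3.2.12 runs opposite to inclusion 3.1.5 and section 1.5.1, the units conflict 10,000-fold, and values from 1.4/1.5 to 2.0 have no settled status

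*Combined protocol and SAP*

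**What the plan says.** Four places in the protocol bear on baseline creatinine.

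- **Section 3.2.12 (exclusion).** The lead-in is "Patients must not have any of the following contraindications to metformin", and one listed item is "Kidney dysfunction or abnormal creatinine (Cr < 2ng/mL) from any cause".
- **Section 3.1.5 (inclusion).** The table sets an upper limit of 1.4 ng/mL for females and 1.5 ng/mL for males. A footnote adds that patients at or below 2.0 ng/mL "may still be eligible if in the opinion of the investigator, the benefits of treatment outweigh the risks".
- **Section 1.5.1 (metformin background).** The contraindications to metformin include "kidney dysfunction (serum creatinine ≥ 1.5 mg/dL in males or ≥ 1.4 mg/dL in females". The unit here is mg/dL.
- **Section 3.0 (how the criteria combine).** "Subjects must meet all of the inclusion and none of the exclusion criteria to be registered to the study". It also says: "Eligibility waivers are not permitted".

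**The concern.** An exclusion meant to keep out patients with poor renal function should carry a threshold that catches high creatinine. The number printed in 3.2.12 catches low creatinine, which 3.1.5 requires. Both are registration criteria, joined by an all-inclusion, no-exclusion rule, so the conflict is not confined to background text.

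By the protocol's own account baseline creatinine is a safety check. Every patient starts metformin at 1,000 mg and escalates toward 2,000 mg as tolerated (section 4.1). Section 4.3.4 says that lactic acidosis is most common with renal insufficiency and congestive heart failure. Section 8.2.8 warns that renal dysfunction caused by iodinated contrast may lead to lactic acidosis associated with metformin, and footnote 8 of Table 5-1 schedules contrast CT every 2 cycles. Under section 11.3 the quality assurance monitor must confirm eligibility before registration. A criterion that cannot be applied as printed leaves that check to interpretation and invites eligibility deviations.

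**Working it through.** No sample size or error rate is involved. The check is an intersection of rules and a unit conversion.

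**Inputs.** Let C be the creatinine value, taken first as a bare number because 3.1.5 and 3.2.12 print the same unit.

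- 3.1.5 admits C ≤ 1.4 (F) or C ≤ 1.5 (M); with discretion, C ≤ 2.0.
- 3.2.12 as printed excludes C < 2.
- 3.0: a patient is eligible only if 3.1.5 admits and 3.2.12 does not exclude.
- 1.5.1 calls C ≥ 1.4 (F) or C ≥ 1.5 (M) a contraindication.

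**Step 1: literal intersection.** Without discretion, {C ≤ 1.4 or 1.5} and {C ≥ 2} have no value in common. With discretion, {C ≤ 2.0} and {C ≥ 2} share the single value C = 2.0.

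**Step 2: other readings of the parenthesis in 3.2.12.**

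| Reading of 3.2.12 | Eligible without discretion | Eligible with discretion |
|---|---|---|
| As printed: exclude C < 2 | none | 2.0 only |
| Sign reversed: exclude C > 2 | ≤ 1.4 (F), ≤ 1.5 (M) | ≤ 2.0 |
| Parenthesis gives the acceptable range: exclude C ≥ 2 | ≤ 1.4 (F), ≤ 1.5 (M) | below 2.0 |

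On the second reading the two criteria agree. On the third they still clash at exactly 2.0, which the 3.1.5 footnote can admit and 3.2.12 would bar.

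**Step 3: does any reading let in creatinine above 2.0?** No. 3.1.5 caps it at 2.0 under every reading.

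**Step 4: overlap with 1.5.1, taking the numerals at face value.** Under either charitable reading:

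- Without discretion, 3.1.5 accepts exactly 1.4 (F) and exactly 1.5 (M). 1.5.1 lists both values as contraindicated.
- With discretion, the whole band above 1.4 (F) or 1.5 (M), up to 2.0, lies inside the range in 1.5.1.

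A patient at 1.8 illustrates this: the 3.1.5 footnote can admit that value, while 1.5.1 describes it as kidney dysfunction, which 3.2.12 bars in words.

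**Step 5: units.** 1 mg = 1,000,000 ng and 1 dL = 100 mL, so 1 mg/dL = 1,000,000 / 100 = 10,000 ng/mL.

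| Numeral | If ng/mL, in mg/dL | If mg/dL, in ng/mL |
|---|---|---|
| 1.4 | 0.00014 | 14,000 |
| 1.5 | 0.00015 | 15,000 |
| 2.0 | 0.0002 | 20,000 |

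The same numerals 1.4 and 1.5 therefore stand for quantities 10,000 times apart in 1.5.1 and 3.1.5. Taken at its word, the ng/mL limit in 3.1.5 would turn away a patient at 1.0 mg/dL (an illustrative value, not from the protocol), since 1.0 mg/dL = 10,000 ng/mL.

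**The case against.** The strongest reply is that this is a visible drafting slip. The number 2 in 3.2.12 matches the 2.0 in the 3.1.5 footnote, so staff can see that 2 is the boundary and would probably apply it the sensible way round. The numerals 1.4 and 1.5 appear with mg/dL in 1.5.1, which makes the unit error easy to spot. The trial is planned at a single institution (section 10.2; section 3.0 mentions only the potential to open elsewhere), and eligibility is confirmed centrally. Much of this stands. A reader might infer from the literal result that the trial could enrol nobody, but that outcome is one of strict logic, and staff would probably read around it. Nor is it a matter of many sites each guessing alone.

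A reader might also infer that the two criteria together fail to exclude renal dysfunction. The documents do not support that: 3.1.5 caps creatinine at 1.4/1.5, or 2.0 with discretion, and 3.2.12 excludes kidney dysfunction in words. Only the parenthetical number fails to screen out high values.

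A third tempting reading is that admitting a patient in the discretionary band directly breaches 3.2.12. That is too strong as well. 3.2.12 bars the items in its own list and does not import the thresholds of 1.5.1, and the shared figure of 2 may reflect a deliberate band of investigator discretion. What remains is an unresolved tension: 3.2.12 bars kidney dysfunction, 1.5.1 is where the protocol puts a range on that term, and neither says which governs.

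Finally, the direction point turns on one inequality character, and the creatinine row of the 3.1.5 table shows conversion damage in the extracted text. The symbol in 3.2.12 should be checked against the approved PDF. The ng/mL unit is less likely to be an artefact, because it recurs in 3.1.5, its footnote and 3.2.12.

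**Conclusion.** The text is wrong as written, in an operative safety criterion. Four defects remain:

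1. The threshold in 3.2.12 runs opposite to 3.1.5 and 1.5.1. Read literally, only exactly 2.0 with discretion meets both criteria.
2. The eligibility criteria print ng/mL and 1.5.1 prints mg/dL, a 10,000-fold difference.
3. If the parenthesis is read as the acceptable range, 3.1.5 and 3.2.12 conflict at exactly 2.0.
4. Values from 1.4 (F) or 1.5 (M) up to 2.0 can be admitted under 3.1.5 and its footnote but are described in 1.5.1 as a metformin contraindication.

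The realistic consequence is inconsistent decisions on patients in that band, under a rule that allows no waivers. The fourth defect survives even if the sign and unit are read charitably, so correcting those two alone would not settle the matter. How many patients it would touch cannot be computed, because the documents give no creatinine distribution. The conclusion assumes that the printed inequality matches the approved protocol. Sample size, endpoint and decision rules are unaffected.

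**What to change.** Reconcile section 1.5.1, section 3.1.5 with its footnote, and section 3.2.12 on four matters:

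- the direction of the threshold, so that inclusion and exclusion can both be satisfied;
- one unit throughout;
- whether exactly 2.0 is in or out;
- whether the discretionary band, and the exact values 1.4 and 1.5, stand against the contraindication described in 1.5.1, and which section governs.

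The clinical team sets the limit; none is proposed here. The eligibility checklist and eligibility eCRF named in section 11.3 should then be brought into line.

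The cost is one eligibility amendment and a checklist update. Amendment 5 already corrected an eligibility discrepancy by this route.

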4.0 TREATMENT PLAN

4.1 Overview

Nivolumab and metformin combination will be administered intravenously and orally, respectively, until disease progression or intolerable toxicity. Metformin will be initiated during a 7-day Induction period at 1,000mg orally once daily. Metformin will then be escalated by 500mg every 7 days as tolerated (C1D1 and C1D8) until the full 2,000mg dose is reached. Extended release formulation - Glucophage XR will be used for the study and commercial supply will be used which will be purchased and dispensed by NU investigational pharmacy. During Cycle 1-4 (1 cycle = 28 days), nivolumab will be given at 240mg every 14 days (Day 1 & 15) over approximately 30 minutes (-5 / +15 minutes). Starting with Cycle 5 Day 1, nivolumab will be given at 480mg IV every 28 days over approximately 60 minutes (-10 / +15 minutes). Patients will be assessed for response every 8 weeks (2 cycles).

Note: Please refer to section 4.4 for patients who may continue treatment after initial progression.

Dosing schedule is summarized in the table below.

Table 4-1: Dosing of Nivolumab and Metformin

Drug	Dose	Route	Schedule
Nivolumab (Opdivo)	C1-4: 240mg C5+: 480mg	IV	Cycle 1-4: every 14 days Cycle 5+: every 28 days until progression of disease, intolerable toxicity, or withdrawal of consent
Metformin hydrochloride (Glucophage XR)	2,000mg*	PO	daily with evening meal until progression of disease, intolerable toxicity, or withdrawal of consent 
 • starting dose: 1,000mg • dose escalation plan: weekly by 500mg

*Metformin will be initiated at 1,000mg during the Induction period and escalate by 500mg (1 tablet) every 7 days until the final dose of 2,000mg.

4.2 Treatment Administration

4.2.1 Nivolumab

Treatment will be administered on an outpatient basis. Reported adverse events and potential risks are described below. No investigational or commercial agents or therapies other than those described below may be administered with the intent to treat the patient's malignancy.

During Cycle 1-4, nivolumab will be administered at a fixed dose of 240 mg intravenously over approximately 30 minutes (-5 / +15 minutes) every 14 days. Starting with Cycle 5, nivolumab will be administered at 480mg IV over 60 minutes (-10 / +15 minutes) every 28 days until disease progression, intolerable toxicity, or withdrawal of consent.

There will be no dose escalations or reductions of nivolumab allowed. Subjects may be dosed no less than 12 days or 24 days from the previous dose (for 240 mg and 480 mg doses, respectively). There are no pre-medications recommended for nivolumab on the first cycle. If an acute infusion reaction is noted, subjects should be managed according to Section 4.3.3.

Nivolumab is to be administered as a 30-minute (-5 / +15 minutes) or 60-minute (-10 / +15± minutes) IV infusion (for 240mg and 480mg respectively), using a volumetric pump with a 0.2- 1.2 micron low-protein binding in-line filter at the

NU Study Number: NU 16L04
Other Study Number: CA 209-801

protocol-specified dose. The drug can be infused undiluted or diluted so as not to exceed a total infusion volume of 120mL. It is not to be administered as an IV push or bolus injection. At the end of the infusion, flush the line with a sufficient quantity of normal saline.

Subjects will be monitored continuously for AEs while on study. Treatment delay or discontinuation will be based on specific laboratory and adverse event criteria.

Early recognition and management may mitigate severe toxicity. Evaluation and Management Guidelines were developed to assist investigators and can be found in the Investigator Brochure:

- Suspected Pulmonary Toxicity
- Diarrhea and Colitis
- Suspected Hepatotoxicity (including asymptomatic liver function tests [LFT] elevations)
- Suspected Endocrinopathy
- Nephrotoxicity

4.2.2 Metformin

Metformin will be administered orally once daily until disease progression, intolerable toxicity or withdrawal of consent. Extended release formulation - Glucophage XR, 500 mg will be used for the study. Two tablets (1,000 mg) PO once daily will be given for the first 7 days, then 3 tablets (1,500 mg) for the next 7 days, then 4 tablets (2,000 mg) for the rest of the treatment period. Metformin should be taken with meals. This dose escalation plan is to minimize possible gastrointestinal toxicity of metformin. 2550mg of metformin is the FDA approved maximum dose of metformin. Tablets should not be cut, crushed, or chewed. Metformin will be held per institutional guidelines with IV contrast dye injection required for each imaging studies. Metformin dosing can occur independently of nivolumab dosing. No premedications are needed.

Patients will maintain a drug diary throughout the study to monitor compliance of metformin dosing. Patients will return completed drug diaries, drug bottles, and any unused metformin tablets at each study visit.

4.3 Toxicity Management & Dose Delays/Modifications

Any patient who receives at least one dose of study therapy will be evaluable for toxicity endpoints. Each patient will be assessed for the development of toxicity according to the timeframe referenced in the Schedule of Events table. Toxicity will be assessed according to the NCI CTCAE v. 4.03.

4.3.1 Dose delays: nivolumab

There will be no dose modifications allowed for management of toxicities. Should the treating physician decide to delay treatment given suspicion for a drug-related side effect, the side effect should be attributed to one study drug to the best of the physician's ability. Nivolumab should be delayed based on this attribution, or both drugs if a definite attribution is not possible. Nivolumab can be held for a maximum of 56 days.

Nivolumab administration should be delayed for the following until resolution to \leq Grade 1 or baseline:

- Any Grade \geq 2 non-skin, drug-related adverse event, with the following exceptions:
 - Grade 2 drug-related fatigue or laboratory abnormalities do not require a treatment delay

NU Study Number: NU 16L04
Other Study Number: CA 209-801

- Any Grade 3 skin, drug-related adverse event
- Any Grade 3 drug-related laboratory abnormality, with the following exceptions for lymphopenia, leukopenia, AST, ALT, or total bilirubin:
 - Grade 3 lymphopenia or leukopenia does not require dose delay
 - If a subject has a baseline AST, ALT or total bilirubin that is within normal limits, delay dosing for drug-related Grade ≥ 2 toxicity
 - If a subject has baseline AST, ALT, or total bilirubin within the Grade 1 toxicity range, delay dosing for drug-related Grade ≥ 3 toxicity

Any adverse event, laboratory abnormality, or intercurrent illness which, in the judgment of the investigator, warrants delaying the dose of study medication.

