4.3.2 Treatment discontinuation: nivolumab

Should the treating physician decide to discontinue treatment given suspicion for a drug-related side effect, the side effect should be attributed to one study drug to the best of the physician's ability. Nivolumab should be discontinued based on this attribution, and the patient must come off study treatment. The patient may not receive metformin monotherapy on-study.

Nivolumab should be discontinued permanently for the following:

- Any Grade 2 drug-related uveitis, eye pain, or blurred vision that does not respond to topical therapy and does not improve to Grade 1 severity within the re-treatment period OR requires systemic treatment
- Any Grade 3 non-skin, drug-related adverse event lasting > 7 days, with the following exceptions for laboratory abnormalities, drug-related uveitis, pneumonitis, bronchospasm, hypersensitivity reactions, infusion reactions, and endocrinopathies:
 - Grade 3 drug-related uveitis, pneumonitis, bronchospasm, hypersensitivity reaction, or infusion reaction of any duration requires discontinuation
 - Grade 3 drug endocrinopathies adequately controlled with only physiologic hormone replacement do not require discontinuation
 - Grade 3 drug-related laboratory abnormalities do not require treatment discontinuation except:
 - Grade 3 drug-related thrombocytopenia > 7 days or associated with bleeding (aside from minor bleeds \leq Grade 1) requires discontinuation
 - Any drug-related liver function test (LFT) abnormality that meets the following criteria require discontinuation:
 - AST or ALT $> 5-10 \times$ ULN for > 2 weeks
 - AST or ALT $> 10 \times$ ULN
 - Total bilirubin $> 5 \times$ ULN
 - Concurrent AST or ALT $> 3 \times$ ULN and total bilirubin $> 2 \times$ ULN
- Any Grade 4 drug-related adverse event or laboratory abnormality, except for the following events which do not require discontinuation:
 - Grade 4 neutropenia < 7 days
 - Grade 4 lymphopenia or leukopenia
 - Isolated Grade 4 amylase or lipase abnormalities that are not associated with symptoms or clinical manifestations of pancreatitis. PI and Data and Safety Monitoring Committee (DSMC) should be consulted for Grade 4 amylase or lipase abnormalities.

NU Study Number: NU 16L04
Other Study Number: CA 209-801

- Isolated Grade 4 electrolyte imbalances/abnormalities that are not associated with clinical sequelae and are corrected with supplementation/appropriate management within 72 hours of their onset

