- Grade 4 drug-related endocrinopathy adverse events, such as adrenal insufficiency, ACTH deficiency, hyper- or hypothyroidism, or glucose intolerance, which resolve or are adequately controlled with physiologic hormone replacement (corticosteroids, thyroid hormones) or glucose-controlling agents, respectively, may not require discontinuation.
- Any event that leads to interruption in dosing lasting > 4 weeks from the previous dose requires discontinuation, with the following exceptions:
 - Dosing interruptions to allow for prolonged steroid tapers to manage drug-related adverse events are allowed. Prior to re-initiating treatment in a subject with a dosing interruptions lasting > 4 weeks from the previous dose, the PI and DSMC must be consulted. Tumor assessments should continue as per protocol even if dosing is interrupted. Periodic study visits to assess safety and laboratory studies should also continue every 4 weeks or more frequently if clinically indicated during such dosing interruptions.
 - Dosing interruptions lasting > 4 weeks from the previous dose that occur for non-drug- related reasons may be allowed if approved by the PI and DSMC. Prior to re-initiating treatment in a subject with a dosing interruption lasting > 4 weeks, the PI and DSMC must be consulted. Tumor assessments should continue as per protocol even if dosing is interrupted. Periodic study visits to assess safety and laboratory studies should also continue every 4 weeks or more frequently if clinically indicated during such dosing interrupted.
 - Any adverse event, laboratory abnormality, or intercurrent illness, which in the judgment of the Investigator, presents a substantial clinical risk to the subject with continued nivolumab dosing.
 - If the patient is still receiving clinical benefit, he or she can hold drug for a maximum of 8 weeks (56 days) and subsequently continue therapy following the original treatment schedule.

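### Sections 4.3.1 and 4.3.2: a hormone-controlled endocrinopathy is spared two stopping rules but gets no exception to the restart condition, so the general interruption limits can still end treatment

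*Combined protocol and SAP*

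**What the plan says.** **Restart (4.3.1).** For listed events, "Nivolumab administration should be delayed for the following until resolution to" Grade 1 or lower, or baseline. The list includes every non-skin drug-related event of Grade 2 or worse. That item has one exception: "Grade 2 drug-related fatigue or laboratory abnormalities do not require a treatment delay". The other exceptions in 4.3.1 concern lymphopenia, leukopenia, AST, ALT and bilirubin. Endocrinopathy is not named. The section also sets an overall cap: "Nivolumab can be held for a maximum of 56 days".

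**Permanent stop (4.3.2).** Among the exceptions to the rule for Grade 3 non-skin events lasting more than 7 days: "Grade 3 drug endocrinopathies adequately controlled with only physiologic hormone replacement do not require discontinuation". Among the exceptions to the Grade 4 rule are endocrinopathies "which resolve or are adequately controlled with physiologic hormone replacement (corticosteroids, thyroid hormones) or glucose-controlling agents, respectively, may not require discontinuation".

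**Interruption limit (4.3.2).** "Any event that leads to interruption in dosing lasting > 4 weeks from the previous dose requires discontinuation", subject to exceptions. One is for tapers: "Dosing interruptions to allow for prolonged steroid tapers to manage drug-related adverse events are allowed". A second is for non-drug-related reasons, with principal investigator and DSMC approval. A further item lets a patient who still has clinical benefit hold drug for up to 56 days and then go on with the original schedule.

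**Consequence for metformin (4.3.2).** Once nivolumab is stopped for a drug-related effect, the patient leaves study treatment: "The patient may not receive metformin monotherapy on-study".

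**The concern.** The exemptions in 4.3.2 treat control on replacement as a reason not to stop nivolumab. The restart rule in 4.3.1 looks only at grade or baseline, and control does not count. A patient whose endocrinopathy is well controlled but still graded above Grade 1 and baseline is therefore kept on by one rule and held by another, and a third rule turns a long enough hold into a permanent stop.

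What is at stake is who stays on treatment. An investigator who relies on the exemption would re-dose. One who follows the restart and interruption rules would hold and then stop both drugs. The same patient could be handled either way.

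**Working it through.** The plan gives no figure to reproduce. The check compares the rules and does arithmetic on intervals.

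1. **Does the plan foresee control without resolution?** The Grade 3 exemption sits under a rule for events lasting more than 7 days. It does any work only if a controlled event can still be Grade 3 after day 7. The Grade 4 sentence offers resolution and control as alternatives. So yes, although neither line says what grade the event has when the next dose is due.

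2. **Does control permit restart?** Under 4.3.1 the condition is Grade 1 or lower, or baseline. The Grade 2 exceptions are fatigue and laboratory abnormalities, so an endocrinopathy recorded only as a Grade 2 laboratory finding is not held. One recorded as a clinical event of Grade 2 or worse is held, with no exception for control.

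3. **When do the limits bite?**
   - 4-week rule: 4 × 7 = 28 days from the previous dose.
   - Cycles 1–4, dosing every 14 days: the limit falls 28 − 14 = 14 days after the held dose was due.
   - Cycle 5 onward, dosing every 28 days: 28 − 28 = 0, so the limit falls on the due date itself. A dose withheld for the event past that date is already beyond 4 weeks.
   - 4.3.1 cap and clinical-benefit hold: 8 × 7 = 56 days.

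4. **Which routes past 4 weeks are open to a drug-related endocrinopathy managed with replacement alone?**

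| Route in 4.3.2 | Open? |
|---|---|
| Prolonged steroid taper | No: physiologic replacement is not a taper |
| Non-drug-related reason | No: the event is drug-related |
| Clinical benefit, up to 56 days | Yes, if the patient has clinical benefit |

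   That leaves 3 − 1 − 1 = 1 route. It lengthens the hold and does not say that the 4.3.1 restart condition is waived.

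5. **Who has clinical benefit?** 4.3.2 does not define the term. In 10.3 the clinical benefit rate counts CR, PR, or SD of at least 12 weeks. 6.2.1 counts irSD, irPR or irCR for the immune-related version. 4.4 gives symptom improvement and tolerance as an example, for treatment after confirmed progression. On the response-based senses, many patients without progression could use the 56 days. On the 10.3 sense, a patient with stable disease could not yet qualify in the first 12 weeks.

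6. **Result.** For a controlled event that stays above Grade 1 and baseline, the text leads to a stop once the interruption passes 28 days from the previous dose (no taper, no clinical benefit), or at the end of a 56-day hold (clinical benefit). 4.3.2 and 4.6 then take the patient off both drugs.

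**The case against.** The best reply is that the rules can be read together. Each exemption in 4.3.2 belongs to one rule: the Grade 3 line waives the 7-day rule, and the Grade 4 line only says that a stop may not be needed. On that reading a controlled event is not stopped at day 7, or at once for Grade 4, but remains subject to the general hold and its limits. A strict restart rule would then be a cautious choice. The point about scope stands, and a reader who infers that 4.3.2 exempts these events from discontinuation altogether goes further than the text. What remains is that the general limits can remove the very patients the exemptions were written to keep, from Cycle 5 as soon as a dose is held past its due date.

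Three further objections stand in part:

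- **Grade.** The documents do not reproduce how CTCAE grades an endocrinopathy on replacement. If control brings the event to Grade 1, there is no conflict. Persistence above Grade 1 at re-dosing is an assumption.
- **Appendix D.** The endocrinopathy chart is a figure not shown. It is tempting to say that the protocol offers no way back to dosing. The documents do not support that, because the chart may offer one. Section 4.3.3 describes the algorithms as help for investigators, and 4.3.1 and 4.3.2 do not point to them for a restart exception, but neither fact shows that the guidance is absent.
- **Clinical-benefit item.** It speaks of continuing on the original schedule without repeating the Grade 1 condition, so it can arguably be read as a route back. The same extracted sub-list also holds a stopping criterion (substantial clinical risk), so its layout is not firm evidence of how the items relate.

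Other sections accept nivolumab alongside replacement: 3.2.4 admits patients with residual autoimmune hypothyroidism on hormone replacement, and 4.5.1 allows adrenal replacement steroids in the absence of active autoimmune disease. This is only mild support, since a settled pre-existing condition is not a new on-study toxicity.

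**Conclusion.** The point holds for the text of 4.3.1 and 4.3.2. An endocrinopathy that is controlled on physiologic replacement, but still above Grade 1 and baseline, is exempt from the Grade 3 7-day rule and may be exempt from the Grade 4 rule. It has no exception to the restart condition. The 28-day limit or the 56-day hold can therefore still force both drugs to stop and largely defeat the exemption.

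This rests on two assumptions: that the event keeps a grade above 1 when controlled, and that the Appendix D chart does not already settle restart. Patients on a prolonged steroid taper have their own exception to the 4-week rule and are outside the point.

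The size is small and cannot be put as a count, because the documents give no endocrinopathy rate or time of onset. A reader might infer a bias in ORR. That is not claimed: 4.7 keeps imaging patients who stop for adverse events before progression and counts a later response. The evaluability exclusion in 6.3 concerns removal from the study for adverse drug reactions, which 4.8 distinguishes from stopping treatment. The fault is minor and affects the dosing of individual patients; correcting it is worthwhile but optional.

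**What to change.** First check the Appendix D endocrinopathy chart and align the wording with it. Then make two additions.

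- **In 4.3.1:** *Drug-related endocrinopathies adequately controlled with only physiologic hormone replacement (or glucose-controlling agents for glucose intolerance) may resume nivolumab without resolution to Grade 1 or baseline; for events that were Grade 3 or 4, the PI (and the DSMC for Grade 4) must be consulted before re-dosing.*
- **In the 4-week exceptions of 4.3.2:** *Interruptions while a drug-related endocrinopathy is brought under such control are allowed up to 56 days, with PI and DSMC consultation before re-initiating.*

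Glucose-controlling agents are included because the Grade 4 sentence in 4.3.2 already names them.

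The cost is two sentences in the next amendment and one check against the chart, with no added visits, tests or patients. The downside is that some patients would restart nivolumab with a controlled but unresolved endocrinopathy. Section 4.3.2 implies that risk but does not expressly accept it for re-dosing, which is why the consultation step is part of the change.
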